13.1 Adverse Events

In accordance with 21 Code of Federal Regulation (CFR) 312.32(b) and International Conference on Harmonisation (ICH) Guidance E2A, an AE is any untoward medical occurrence in a clinical investigation of a subject administered a pharmaceutical product and that does not necessarily have a causal relationship with the treatment.

An AE is therefore any unfavorable and unintended sign (including an abnormal laboratory finding), symptom, or disease temporally associated with the administration of an investigational product, whether or not related to that investigational product. An unexpected AE is one of a type not identified in nature, severity, or frequency in the current Investigator's Brochure or of greater severity or frequency than expected based on the information in the Investigator's Brochure. Examples of an AE include:

- Significant worsening or exacerbation of underlying medical condition.
- Significant abnormal findings from physical exams, vital signs, or laboratory tests.

The following examples are not considered AE:

- Medical or surgical procedure, although the condition leading to the procedure is usually an AE.

- Anticipated day-to-day fluctuations of preexisting medical conditions (including laboratory values) as long as significant worsening from baseline does not occur.
- Signs or symptoms of the disorder being studied unless they become more severe or occur with greater frequency than occurring at baseline.
- Normal progression of the disorder being studied unless it is more severe per Investigator judgment or occurs with greater speed/frequency than expected.

All AE, whether elicited by questions from study staff, volunteered, or noted on physical examination/laboratory testing, and regardless of causality or severity, will be assessed and recorded in the eCRF beginning after the first administration of study drug in the double-blind period of the study and ending at the time of study completion or ET of the double-blind period or the OLE period, whichever is later.

For patients participating in the OLE period, AE will be recorded in the CRF of the AK002-021 double-blind treatment period database up until the start of the first open-label infusion after the Day 176 visit and recorded in the CRF of the AK002-021 OLE period database beginning from the start of the first open-label infusion after the Day 176 visit.

13.2 Serious Adverse Events

A SAE is defined as an AE that meets that one of the following criteria:

- Death
- A life-threatening AE that places the subject at risk of death at the time of the event. It does not refer to an event that hypothetically might cause death if it were more severe.
- Inpatient hospitalization or prolongation of existing hospitalization.
- A persistent or significant disability/incapacity.
- A congenital anomaly/birth defect occurring in the offspring of a study subject.
- Other important medical events may also be considered a SAE when, based on appropriate medical judgment, they jeopardize the patient or require intervention to prevent one of the outcomes listed above.

The date that an AE meets 1 of the criteria listed above is the date that it becomes an SAE. Conversely, the date that the SAE no longer meets 1 of the criteria listed above is the end date of the SAE. A new AE with an outcome of “recovering” may be created to address the ongoing AE once it is no longer considered serious.

Serious adverse events will be assessed and recorded beginning after the first administration of study drug in the double-blind period of the study and ending at the time of study completion or ET of the double-blind period or the OLE period, whichever is later.

If the SAE is related to a screening procedure, it will be captured from the date of informed consent.

13.3 Adverse Events of Special Interest

Adverse events of special interest (AESI) for this study include:

- Malignancies confirmed by histopathological report. Mast cells and eosinophils are part of the normal immune response. By decreasing their function, AK002 could theoretically increase the risk of malignancy.
- Parasitic infections confirmed by positive clinical laboratory test. (Eosinophils are believed to be involved in protecting the body from parasitic infections. Decreasing their function could theoretically increase the risk of parasitic and opportunistic infections.)
- Opportunistic infections (infections known to be more severe or occur more frequently in immunosuppressed populations) as confirmed by positive clinical laboratory test.
- Infusion-related reactions and hypersensitivity reactions, including anaphylaxis.

Adverse events of special interest will be assessed beginning after the time of the first infusion of study drug in the double-blind period of the study and ending at the time of study completion or ET of the double-blind period or the OLE period, whichever is later. Any new AESI or new information related to a previously reported AESI must be recorded in the AE eCRF and designated as an “AE of special interest.”

13.4 Infusion-Related Reactions

All AE considered by the Investigator *to be related to the infusion* of the biological substance and occurring within 24 hours of the start of the study drug infusion should be captured as 1 AE, termed “IRR.” Common symptoms of IRR include but are not limited to:

- Flushing
- Chills
- Back or abdominal pain
- Chest discomfort or tightness
- Dizziness
- Shortness of breath
- Headache
- Hypotension or hypertension
- Nausea
- Vomiting
- Sweating
- Fever
- Urticaria
- Pruritus
- Bronchospasm

All symptoms experienced by a patient during an IRR will be listed in the eCRF under 1 IRR, unless the Investigator believes a symptom is not part of the IRR, in which case it will be recorded separately. The start time of the IRR will be captured as the start time of the first symptom and the end time of the IRR will be captured as the end time of the last symptom.

Any medications used within 24 hours of an infusion for the treatment of an IRR are not considered prohibited medications.

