13.5 Anaphylaxis

A suspicion of anaphylaxis will be carefully monitored and treated according to standard of care. Emergency crash cart equipment and medications, including multiple doses of epinephrine, vasopressors, and bronchodilators, will be available at all times during the conduct of the study.

To define anaphylactic reactions in a consistent and objective manner, all AE of suspected anaphylaxis will be evaluated using Sampson's Criteria for Anaphylaxis ([Appendix 6](#)).

The assessment of an AE will be done pursuant to definitions set forth by ICH Good Clinical Practice (GCP) guidelines and applicable regulatory requirements.

If a patient experiences signs or symptoms of anaphylaxis, they should be treated with standard of care, such as diphenhydramine, acetaminophen, methylprednisolone, epinephrine, and other supportive measures along with cessation of the infusion.

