13.6 Evaluating Adverse Events and Serious Adverse Events

13.6.1 Establishing Diagnosis

Whenever possible, diagnoses should be given when signs and symptoms are due to a common etiology (e.g., dysuria, urinary nitrites should be reported as a urinary tract infection). If the diagnosis is not known, individual signs and symptoms should be assessed and recorded in the AE eCRF as separate AE. The Investigator (or qualified Subinvestigator) must assign the following AE attributes listed below and is responsible for ensuring this information is recorded in the source documentation.

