19.6 Appendix 6: Sampson's Criteria of Anaphylaxis

ANAPHYLAXIS: Sampson's definition of anaphylaxis (clinical definition) is the acute onset of illness (minutes to several hours) which involves **SKIN, MUCOSAL TISSUE, or BOTH** (e.g., generalized hives, pruritus or flushing, swollen lips-tongue uvula) **with 1 OR more of the following** (Sampson, 2006):

- **RESPIRATORY:** Airway compromise (e.g., dyspnea, wheeze, or bronchospasm, stridor, reduced PEF, hypoxemia)
- **CIRCULATORY:** Reduced blood pressure or associated symptoms of end-organ dysfunction (e.g., hypotonia, syncope)

OR

2 or MORE of the following that occur rapidly after exposure:

- **SKIN, MUCOSAL TISSUE:** e.g., generalized hives, itch-flush, swollen lips-tongue-uvula
- **RESPIRATORY:** Airway compromise (e.g., dyspnea, wheeze, or bronchospasm, stridor and reduced PEF)
- **CIRCULATORY:** Reduced blood pressure or associated symptoms of end-organ dysfunction (e.g., hypotonia, syncope)
- **GASTROINTESTINAL:** Persistent gastrointestinal symptoms (e.g., crampy abdominal pain, vomiting, nausea, diarrhea)

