## 6.15 Safety Analyses

### 6.15.1 Adverse Events

Safety assessments will be based mainly on the nature, frequency, relationship, and severity of adverse events (AE). The AE will be coded by primary System Organ Class (SOC) and Preferred Term (PT) according to MedDRA (version 21.0). The treatment-emergent adverse events (TEAE) will be summarized by the number and percentage (n and %) of subjects in each SOC and PT.

For summaries by relationship to study drug, “possibly related” will be combined with “related”, and “unlikely/remotely related” will be combined with “not related.” When multiple AE are reported with the same PT, the AE of the strongest relation to study drug will be included in the summary by relationship, and the AE of the most severe grade will be included in the summary by severity table.

The following AE incidence tables will be presented.

- Overview of TEAE to include
  - Number (%) of subjects who reported at least 1 TEAE
  - Number (%) of subjects who reported at least 1 treatment-related TEAE
  - Number (%) of subjects who reported at least 1 severe TEAE
  - Number (%) of subjects who reported at least 1 serious TEAE
  - Number (%) of subjects who reported at least 1 TEAE leading to treatment discontinuation
  - Number (%) of subjects who reported at least 1 TEAE leading to study discontinuation
  - Number (%) of subjects who reported at least 1 TEAE of special interest (TEAESI)
- TEAE by PT sorted by decreasing order of subject incidence in the combined treatment group
- TEAE by SOC and PT in alphabetical order
- TEAE by SOC, PT, and maximum severity
- TEAE by SOC, PT, and strongest relationship to study drug
- TEAE leading to treatment discontinuation by SOC and PT, if warranted by sample size
- TEAE leading to study discontinuation by SOC and PT, if warranted by sample size
- Serious TEAE by SOC and PT, if warranted by sample size
- TEAESI by SOC and PT

All AE will be listed with onset/stop day, relationship to study drug, severity, action taken, and outcome. Pertinent subject information including treatment group and demographics will also be included.

Separate listings will be provided for TEAE leading to study discontinuation, TEAE of special interest, and treatment-emergent serious AE (TESAE).

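### The plan does not settle whether an infusion reaction that meets its own anaphylaxis criteria is recorded as IRR or as anaphylaxis, so the planned tables give no reliable anaphylaxis incidence by arm

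*Protocol*

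**What the plan says.** **Recording.** Protocol 13.4 covers adverse events that the Investigator considers infusion-related. Those "occurring within 24 hours of the start of the study drug infusion should be captured as 1 AE, termed" IRR. On the component symptoms it says: "All symptoms experienced by a patient during an IRR will be listed in the eCRF under 1 IRR". The one exception is "unless the Investigator believes a symptom is not part of the IRR, in which case it will be recorded separately".

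**Anaphylaxis.** Protocol 13.5 says that "all AE of suspected anaphylaxis will be evaluated using Sampson's Criteria for Anaphylaxis", which are set out in Appendix 6. Its stated purpose is a consistent and objective definition. It does not say whether a positive result changes the recorded term, sets a flag or enters an analysis.

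**Diagnosis.** Protocol 13.6.1 gives the general rule: "Whenever possible, diagnoses should be given when signs and symptoms are due to a common etiology".

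**Special interest.** Protocol 13.3 places three things in one category: "Infusion-related reactions and hypersensitivity reactions, including anaphylaxis".

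**Output.** SAP 6.15.1 plans "TEAESI by SOC and PT", as does Protocol 15.7.1. SAP Appendix 3 carries this through to Tables 14.3.1.8a and 14.3.1.8b, with one listing for all events of special interest (16.2.3.1.5). The SAP text does not mention anaphylaxis.

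**The concern.** AK002 is an infused antibody whose most common treatment-emergent event is IRR (Protocol 2.3), and anaphylaxis is a named event of special interest. The protocol collects evidence on it: an evaluation against set criteria, and histamine and tryptase samples when it is suspected (11.5.6). A reader of the study report would expect to learn how many patients in each arm met the criteria.

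The planned tables may not say. If the 13.4 rule is followed literally, a reaction with urticaria and bronchospasm appears on the same IRR line as a brief episode of flushing. If some sites follow 13.4 and others follow 13.6.1, the anaphylaxis line counts only the cases that happened to be entered as a diagnosis. In either case a small or zero figure on that line could be misread as the incidence.

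**Working it through.** The documents state no anaphylaxis or IRR rate, and no sample size rests on one, so there is no planned figure to reproduce. The check traces one event from recording to output.

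**1. Can an IRR meet the anaphylaxis criteria?** Appendix 6 has two routes. The first is acute skin or mucosal involvement with respiratory or circulatory compromise. The second is "2 or MORE of the following that occur rapidly after exposure", from four groups. The IRR symptom list in 13.4 covers all four:

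| Appendix 6 group | IRR symptoms listed in 13.4 |
|---|---|
| Skin, mucosal | urticaria, pruritus, flushing |
| Respiratory | bronchospasm, shortness of breath |
| Circulatory | hypotension |
| Gastrointestinal (persistent) | abdominal pain, nausea, vomiting |

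An acute reaction with urticaria plus bronchospasm or hypotension meets the definition using only symptoms that 13.4 calls common in an IRR.

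**2. Which term is recorded?** Under 13.4 it is IRR, because the only exception removes a symptom that is not part of the reaction. Under 13.6.1 it could be anaphylaxis, as a diagnosis. Section 13.5 is silent on the term. The 13.4 rule is specific to infusion events and 13.6.1 is general, but no text ranks them.

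**3. Is every qualifying event classified?** Section 13.5 is triggered by suspicion. An IRR that meets Appendix 6 without being suspected need not be evaluated.

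**4. What reaches the tables?** Under either term the event is of special interest and enters the table. The preferred term decides the line. No row counts events meeting Appendix 6 whatever their term.

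**5. Illustration.** Take 40 per arm (Protocol 7.1). The event counts are assumptions. Exact two-sided 95% limits (Clopper-Pearson):

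| Events meeting the criteria | Incidence | 95% CI |
|---|---|---|
| 0/40 | 0% | 0 to 8.8% |
| 1/40 | 2.5% | 0.06 to 13.2% |
| 2/40 | 5.0% | 0.6 to 16.9% |

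For 0/40 the upper limit is 1 − 0.025^(1/40) = 0.088. If the only qualifying event is recorded as IRR, the anaphylaxis line moves from the second row to the first.

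The chance of at least one event among 40 treated patients is 1 − (1 − p)^40. For assumed true rates p of 0.5%, 1%, 2% and 5% it is 18%, 33%, 55% and 87%. The question may well arise in this trial, but the documents do not say how likely that is.

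**The case against.** The strongest reply is that relabelling is not compelled. Read together, 13.3 names anaphylaxis, 13.5 treats it in its own section, and 13.6.1 asks for a diagnosis. On that reading an event meeting the criteria is reported as anaphylaxis, and 13.4 serves only to stop flushing, headache and nausea being entered as separate events. This is a fair reading, but it is not written down, and 13.4 contains no exemption. What stands is that misclassification is possible, not certain.

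Second, the information is kept. Symptoms are listed under the IRR, SAP 5.1 commits to listing all eCRF data, all adverse events and events of special interest have listings, and an event that is serious also goes through SAE reporting. The eCRF is not among the documents and may already hold a field for the criteria. This stands too. A reader might infer that the anaphylaxis rate is lost or could never be stated; the documents do not support that. They show only that no planned summary reports it.

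Third, the severity table and SAE outputs might be thought to fill the gap. They do not: the IRR grades in Protocol Appendix 4 rest mainly on intervention and duration, not on organ systems, and seriousness is a different criterion from Appendix 6.

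Fourth, the trial could not compare arms anyway. Protocol Section 15 plans no formal inference for safety, and 2/40 against 0/40 gives a two-sided Fisher p of 2 × C(40,2)/C(80,2) = 2 × 780/3160 = 0.49. This is correct, and the point does not depend on a test. It concerns a descriptive count being right.

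**Conclusion.** The point holds as a gap between a recording rule and an analysis rule. Section 13.4 gives infusion-related events one term with no exemption, 13.5 and 13.6.1 point towards a separate classification, nothing ranks them, and the SAP counts only by preferred term. The preferred-term count of anaphylaxis is therefore unreliable, which defeats the aim of consistency in 13.5.

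It would go too far to say that every qualifying event will be labelled IRR, or that the table will show zero. That needs all sites to follow 13.4 over 13.6.1 in every case, which the documents do not establish.

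The size cannot be fixed. One event is 2.5% of an arm of 40, and the difference between 2.5% and 0% is an example, not an estimate. No efficacy result is affected, and suspected anaphylaxis is evaluated under 13.5 whichever term is entered. This is a cheap improvement.

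**What to change.** 1. **Protocol 13.4, 13.5 and 13.6.1.** State, for recording purposes only, how an infusion reaction that meets Appendix 6 is entered, so that all sites use the same term.
2. **Data.** Record a yes/no result against Sampson's criteria for each IRR or hypersensitivity event, suspected or not. Alternatively, derive it under blind from the symptoms already listed under each IRR. The field is the safer choice: Appendix 6 turns on rapid onset and persistence, whereas 13.4 asks only for the start of the first symptom and the end of the last.
3. **SAP 6.15.1 and Appendix 3.** Add the number and percentage of patients per arm with an event meeting the criteria, whatever the reported term, with an exact two-sided 95% CI and a listing.

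The cost is a sentence or two in the protocol, one field or derived variable, one table row and one listing. The reported anaphylaxis rate may be less favourable than a count by preferred term. Clinical management does not change.

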13.5 Anaphylaxis

A suspicion of anaphylaxis will be carefully monitored and treated according to standard of care. Emergency crash cart equipment and medications, including multiple doses of epinephrine, vasopressors, and bronchodilators, will be available at all times during the conduct of the study.

To define anaphylactic reactions in a consistent and objective manner, all AE of suspected anaphylaxis will be evaluated using Sampson's Criteria for Anaphylaxis ([Appendix 6](#)).

The assessment of an AE will be done pursuant to definitions set forth by ICH Good Clinical Practice (GCP) guidelines and applicable regulatory requirements.

If a patient experiences signs or symptoms of anaphylaxis, they should be treated with standard of care, such as diphenhydramine, acetaminophen, methylprednisolone, epinephrine, and other supportive measures along with cessation of the infusion.

13.6 Evaluating Adverse Events and Serious Adverse Events

13.6.1 Establishing Diagnosis

Whenever possible, diagnoses should be given when signs and symptoms are due to a common etiology (e.g., dysuria, urinary nitrites should be reported as a urinary tract infection). If the diagnosis is not known, individual signs and symptoms should be assessed and recorded in the AE eCRF as separate AE. The Investigator (or qualified Subinvestigator) must assign the following AE attributes listed below and is responsible for ensuring this information is recorded in the source documentation.

13.6.2 Assessment of Intensity

Investigators will use their clinical judgment as well as the guidelines laid out in the NCI CTCAE (version 5.0 or most current version) tables to assess the intensity of each AE and SAE (Table 3 and [Appendix 4](#)).

Table 3 Adverse Event Severity per CTCAE

Grade	CTCAE Description*
1	Mild; asymptomatic or mild symptoms; clinical or diagnostic observations only; intervention not indicated.
2	Moderate; minimal, local or noninvasive intervention indicated; limiting age appropriate instrumental activities of daily living (ADL).
3	Severe or medically significant but not immediately life-threatening, hospitalization or prolongation of hospitalization indicated; disabling; limiting self-care ADL.
4	Life-threatening consequences, urgent intervention indicated.
5	Death related to AE.

* CTCAE v. 5.0: Grade refers to the severity of the AE. The CTCAE displays Grades 1–5 with unique clinical descriptions of severity for each AE based on this general guideline.

The term “severe” is a measure of intensity, and a severe AE is not necessarily a SAE.

When the intensity of an AE changes more than once a day, the maximum severity for the event should be entered into the AE eCRF. If the intensity changes over a number of days, these changes should be recorded separately (i.e., as having distinct onset dates).

13.6.3 Assessment of Causality to Study Drug

The Investigator should use their clinical judgment as well as the guidelines in [Table 4](#) to assess the relationship between study drug and AE.

Table 4 Adverse Event Relationship to Study Drug

Relationship to Study Drug	Comment
Related	There is clear evidence that the event is related to the use of study drug (e.g., confirmation by positive re-challenge test, if possible). Another etiology is considerably less likely.
Possible	The event cannot be explained by the subject's medical condition, concomitant therapy, or other causes, and there is a plausible temporal relationship between the event and study drug administration.
Unlikely/Remote	An event for which an alternative explanation is more likely (e.g., concomitant medications or ongoing medical conditions) or the temporal relationship to study drug administration and/or exposure suggests that a causal relationship is unlikely. (For reporting purposes, Unlikely/Remote will be grouped together with Not Related.)
Not Related	The event can be readily explained by the subject's underlying medical condition, concomitant therapy, or other causes, and therefore, the Investigator believes no relationship exists between the event and study drug.

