13.6.4 Assessment of Causality to Study Procedure

The Investigator should use their clinical judgment as well as the guidelines in Table 5 to assess the relationship between study procedure and AE. Assessment of Causality to Study Procedure should include causality to such items as EGD with biopsy or blood draw (as appropriate), or other.

Table 5 Adverse Event Relationship to Study Procedure

Relationship to Study Procedure	Comment
Related	There is clear evidence that the event is related to a study procedure.
Possible	The event cannot be explained by the subject's medical condition, concomitant therapy, or other causes, and there is a plausible temporal relationship between the event and a study procedure.
Unlikely/Remote	An event for which an alternative explanation is more likely (e.g., concomitant medications or ongoing medical conditions) or the temporal relationship to any study procedure suggests that a causal relationship is unlikely (For reporting purposes, Unlikely/Remote will be grouped together with Not Related).
Not Related	The event can be readily explained by the subject's underlying medical condition, concomitant therapy, or other causes, and therefore, the Investigator believes no relationship exists between the event and a study procedure.

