13.7.2 Serious Adverse Event Reporting

In the event of any SAE reported or observed during the study, whether or not attributable to the study drug, site personnel must report it immediately (**within 24 hours of becoming aware of the SAE**) by telephone or email to the Sponsor, Allakos Inc.

The SAE report forms will be provided to the investigational site to assist in collecting, organizing, and reporting SAE, and forms must be completed with as much information as is available and should be submitted to the Sponsor within 24 hours of becoming aware of the event. Serious adverse events must also be recorded on the AE eCRF and designated as “serious.”

Even when only minimal information is available for the initial SAE report, the Investigator should try to make a causality assessment, as the causality is used to determine the timing of regulatory reporting requirements. If the Investigator or designee is not available to sign the SAE report on initial submission, they should be contacted by telephone and their assessment documented on the SAE form (with a note stating signature is forthcoming). The Investigator **may change** their causality assessment based on follow-up information and submit an amended SAE report form.

All efforts will be made to obtain accurate and complete medical records for the SAE. All efforts to obtain information should be documented in the patient source documents.

The site will notify the IRB according to its guidelines.

The patient's condition will be followed by the Investigator or designated Subinvestigator until resolution of the condition or a return to baseline levels. If additional visits are required, the patient will be asked to return to the study site for further follow-up. If the condition is still ongoing at the time the patient exits the study, every effort will be made to continue to follow up with the patient for a reasonable period of time, as determined by the Investigator or until there is a return to baseline or stabilization of the condition. As additional information becomes available, such as hospital discharge notes and patient medical records, the Investigator will be notified and provided with all relevant information.

All SAE that have not resolved by the end of the study or that have not resolved on discontinuation of the patient's participation in the study must be followed until any of the following occurs:

- The event resolves.
- The event stabilizes.

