13.11 Study Stopping Rules

The study may be discontinued prematurely in the event of any of the following:

- A life-threatening AE that is possibly or probably related to treatment.
- A fatal AE that is possibly or probably related to treatment.
- New information leading to unfavorable risk-benefit judgment of the study drug.
- Sponsor's decision that continuation of the trial is unjustifiable for medical or ethical reasons.
- Discontinuation of development of the Sponsor's study drug.

Health Authorities and IRB will be informed about the discontinuation of the study in accordance with applicable regulations. The study may be terminated or suspended on request of Health Authorities or Sponsor.

14. Discontinuation and Replacement of Patients

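### In Protocol Tables 4 and 5, 'Possible' is ruled out by any other explanation, so a plausibly timed event that drug and disease explain about equally well meets no drug-related grade

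*Protocol*

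**What the plan says.** Protocol 13.6.3 tells the investigator to use clinical judgment together with Table 4, which has four grades.

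- **Related**: "There is clear evidence that the event is related to the use of study drug", and "Another etiology is considerably less likely".
- **Possible**: "The event cannot be explained by the subject's medical condition, concomitant therapy, or other causes", and in addition "there is a plausible temporal relationship between the event and study drug administration".
- **Unlikely/Remote**: another explanation outweighs the drug, or the timing or exposure argues against a causal link.
- **Not Related**: "The event can be readily explained by the subject's underlying medical condition, concomitant therapy, or other causes", and the investigator for that reason believes there is no relationship.

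Table 5 (Protocol 13.6.4) defines 'Possible' for study procedures in the same way: no other explanation, and "there is a plausible temporal relationship between the event and a study procedure".

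The four grades are reported as two groups. Table 4 places Unlikely/Remote with Not Related, and SAP 6.15.1 also combines Possible with Related. Protocol 13.7.2 says that "the causality is used to determine the timing of regulatory reporting requirements". The AE-based stopping criteria in Protocol 13.11 use different terms, for example "A fatal AE that is possibly or probably related to treatment"; the life-threatening criterion is worded the same way.

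**The concern.** A causality scale should run in order: as the case for the drug weakens, the grade steps down. In Table 4 the second grade is harder to meet than the first on the question of alternative causes. 'Related' can stand beside a rival explanation if that rival is much weaker; 'Possible' cannot stand beside any rival. The middle ground, where drug and disease are both credible, has no drug-related grade.

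That middle ground is realistic in this trial. The protocol lists abdominal pain, nausea and vomiting as symptoms of EoD (Section 2.4) and also as common symptoms of infusion-related reactions (Section 13.4). Inclusion criterion 5 requires abdominal pain, nausea or diarrhea averaging at least 3 for at least 2 screening weeks. When such a symptom worsens on treatment, the underlying disease is often a credible rival explanation.

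At stake are the treatment-related TEAE summaries, the timing of regulatory reports, and the meaning of 'possibly' in 13.11, which takes its definition from Table 4.

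**Working it through.** No arithmetic applies: the point depends on no sample size, rate or power figure, and the plan states no figure to reproduce. The check is to take events with plausible timing and test each against the literal conditions in Table 4.

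| Event (plausible timing) | Related | Possible | Unlikely/Remote | Not Related |
|---|---|---|---|---|
| A. Clear evidence for the drug; rival cause much weaker | fits | fails: a rival exists | fails | fails |
| B. Drug somewhat more likely; evidence not clear; rival credible | fails: no clear evidence | fails: a rival exists | fails: rival does not outweigh the drug | fails: no belief that a relationship is absent |
| C. Drug and disease about equally likely | fails: no clear evidence, rival not much weaker | fails: a rival exists | fails: rival does not outweigh the drug | fails: no belief that a relationship is absent |
| D. Rival more likely than the drug | fails | fails | fits | only if the investigator believes there is no relationship |
| E. No other explanation; evidence for the drug not clear | fails: no clear evidence | fits | fails | fails |

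Four results follow.

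1. Events B and C meet 0 of the 2 drug-related grades and, read strictly, 0 of the 4 grades.
2. The scale is not ordered. Event A has a rival cause and can be 'Related', yet that same rival would bar it from 'Possible'.
3. If a grade has to be chosen for B or C, the only wording that addresses an explainable event lies in the two grades reported as not related. An investigator following the text may therefore put the event there. Another may use judgment and choose 'Possible'. With approximately 35 sites (Protocol 7.2), grading may differ.
4. SAP 5.4.3 counts an AE with a missing relationship as related. An event left ungraded is thus handled more conservatively than event C placed in the not-related group.

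For the stopping criteria, the terms compare as follows.

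| Term | Table 4 | SAP 6.15.1 | Protocol 13.11 |
|---|---|---|---|
| Possible/possibly | yes | yes | yes |
| Probable/probably | no | no | yes |
| Related as a grade | yes | yes | not named |

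One of the two terms in 13.11 has no counterpart on the scale, and the top grade on the scale is not named in 13.11.

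**The case against.** The case against is substantial, and much of it limits the point.

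- **Table 4 is guidance.** It is used with clinical judgment, so an investigator may still choose 'Possible' for a tie. This stands as mitigation. It also means that judgment must override the text, and it does so without a common rule.
- **The direction of bias is not fixed.** A reader might infer that the table systematically drives tied events to 'Not Related'. The documents do not support that: the grade also requires a belief that no relationship exists, which someone who sees a tie does not hold. The text produces ambiguity with a likely lean, not an automatic assignment.
- **The affected band is limited.** A reader might infer that every AE with a competing explanation is affected. Events A and D show otherwise.
- **Not every GI event is a tie.** Under Protocol 13.1, symptoms of the study disease are not AEs unless they become more severe or more frequent than at baseline. Inclusion criterion 5 needs only one of three symptoms. Events within 24 hours of infusion start that the investigator considers infusion-related are recorded as one IRR (13.4) and tabulated among AEs of special interest. Other events still depend on Table 4.
- **Consequences are buffered.** SAEs go to the sponsor within 24 hours whatever their attribution (13.7.2) and to the IRB regardless of causality (17.2). TEAEs are also tabulated by arm without regard to causality. These protections stand.
- **Section 13.11 is discretionary.** A reader might infer that a fatal drug-related event could escape it. The section says only that the study may be discontinued, already includes 'possibly', and lists grounds that need no causality grade, such as new information on risk and benefit. Reading it to exclude 'Related' is strained.

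**Conclusion.** The defect in the definition of 'Possible' holds on the wording of Tables 4 and 5, and it should be corrected. It affects plausibly timed events for which a rival cause is credible but does not outweigh the drug, and for which evidence is short of clear. For those events neither drug-related grade is available, so treatment-related TEAEs can be understated and regulatory timing affected.

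The size cannot be computed: the documents give no frequency for such events. The conclusion assumes that at least some investigators grade by the text. It does not touch the all-causality comparison between arms, SAE reporting to the sponsor, or any efficacy analysis. The mismatch of terms in 13.11 is real but of lesser weight.

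**What to change.** In Tables 4 and 5, redefine 'Possible' as a plausible temporal relationship where the study drug (or procedure) cannot be ruled out as a cause, even though the medical condition, concomitant therapy or another cause could also explain the event. Keep 'Unlikely/Remote' for events where the alternative is more likely or the timing argues against a link. The grouping in SAP 6.15.1 can stay as it is.

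Separately, reconcile Protocol 13.6.3, Protocol 13.11 and SAP 6.15.1 to one set of grades. Which grades should count toward stopping is for the sponsor to decide; the need is only that the terms match the scale.

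The cost is revised wording and a memo to sites, with no change to sample size, visits or efficacy analysis. The downside is that somewhat more events will be graded drug-related in both arms.
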